Sepsis is a common life-threatening condition where early antibiotic treatment is an important factor in determining survival¹. For patients with suspected sepsis, it is recommended that antibiotics are commenced within 1 hour, an NHS standard incentivised by a payment framework². However, once commenced, the duration of antibiotic treatment is less certain, as identified within the brief for this call. Fixed duration antibiotic courses are widely used in the NHS because clinical signs and microbiology culture tests are not useful to monitor treatment efficacy to guide the decision to stop antibiotics³. Readily available circulating serum proteins such as C-reactive protein (CRP) and procalcitonin (PCT) are often raised in sepsis and usually fall in response to effective antibiotic treatment⁴. This provides a potential opportunity to personalise antibiotic duration which could lead to reductions in population antibiotic burden, adverse effects for patients, improved healthcare resource utilisation and downstream effects relating to antimicrobial resistance - an urgent priority. Biomarker-guided antibiotic discontinuation protocols in sepsis have been associated with shorter treatment durations in other healthcare systems internationally^{5,6}, but according to NICE, studies are low quality and with uncertain relevance to NHS practice.

The ADAPT-Sepsis trial is a randomised controlled trial to determine the clinical and cost-effectiveness of both CRP and PCT-guided antibiotic duration, using discontinuation protocols, when compared with standard practice in hospitalised adults with sepsis. A more detailed explanation of the background, rationale, and intervention and trial design can be found in the protocol paper. A brief overview of the trial is presented in this paper.

This paper presents the statistical analysis plan for the ADAPT-Sepsis trial which has been developed in line with published guidelines and the planned cost-effectiveness analysis.

Objectives

The primary objective of this trial is to determine whether treatment protocols based on monitoring CRP or PCT in hospitalised adult patients with suspected sepsis reduces the duration of antibiotic therapy

(superiority) while maintaining treatment safety (non-inferiority) as measured by 28-day mortality. A supplementary objective is to estimate the relative cost-effectiveness of each protocol.

Study methods

Trial design

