- Number of randomised patients included in the final analyses at the primary endpoint(s)

Withdrawal and follow-up

Participants may be discontinued from the trial at any time. They can either withdraw from the intervention alone but remain on follow-up or they can withdraw completely from the trial. Unless a participant explicitly withdraws their consent, they will be followed-up wherever possible and data collected as per the protocol until the end of the trial. The number of withdrawals from the trial will be summarised by treatment arms, that is, how many participants withdrew from intervention alone but remained on follow-up and how many withdrew completely from the trial. In addition, the withdrawal timings will also be summarised by treatment arms. It will include withdrawals after randomisation but before hospital discharge, and withdrawals after hospital discharge but before 28 days follow-up. The withdrawal decision i.e. decision made by the participant, consultant, clinical team, antibiotic stopped due to futility, required >21 days of antibiotics post randomisation and

other, will be summarised by treatment arms. Follow-up rates will be computed at the 28-day and 90-day follow-up time-points. At 90 days, only all-cause mortality data will be collected using NHS digital and the Intensive Care National Audit and Research Centre.

Baseline patient characteristics

The baseline demographic characteristics and pre-randomisation clinical measures of all randomised participants will be summarised by treatment arms. Moreover, important process data (e.g. date and time of hospital admission and ICU/HDU admission) will also be collected and summarised by treatment arms. Continuous data will be summarised using the statistics the number of participants (n), mean, standard deviation (sd), median and interquartile range (IQR) whereas categorical data will be summarised using the statistic the number (%) of participants. The table below lists the demographic, clinical measures and process variable data that will be collected and summarised.

- Age
- Gender
- Suspected septic shock
- Surgery within last 72 hours
- Core body temperature
- White cell count
- Critical care admission category
- Critical care origin
- Initial care bundle
- qSOFA score
- SOFA score
- APACHE II score
- Infection data:
 - Community/hospital acquired infection
 - Site of infection
 - Causative microorganism identified for infection
 - If yes to the above, detail pathogen

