- Process of care/adherence variables:

Time from:

- Hospital admission to ICU/HDU admission
- Hospital admission to first diagnosis of suspected sepsis or suspected septic shock
- Randomisation to first research blood sample taken
- First blood sample taken to first blood sample delivered to laboratory

Analysis

Outcome definitions

The primary outcomes of the trial are (i) total duration of antibiotic treatment to 28 days following randomisation (superiority) measured in days as primary clinical effectiveness outcome, and (ii) 28-day all-cause mortality (non-inferiority) following randomisation as primary safety outcome. For the clinical effectiveness outcome, the use of antibiotics data will be recorded to the point where the participant stopped antibiotics. The use of antibiotics will also be recorded if participants either restarts antibiotics in hospital or discharged from hospital and the re-admitted and receives systemic antibiotics or discharged with antibiotics provided that these events are within 28 days following randomisation. The duration of antibiotics use will be calculated for each participant as the sum of the duration of each course of antibiotics administered from randomisation to day 28. For the safety outcome, all-cause mortality status on day 28 following randomisation will be recorded.

The Secondary effectiveness and safety outcome measures to 28 days following randomisation are

- Antibiotic duration and dose for the initial sepsis episode (duration in days from randomisation and dose measured as Defined Daily Dose)
- Antibiotic dose (measured as Defined Daily Dose)
- Unscheduled care escalation/re-admission
- Infection relapse/recurrence requiring further antibiotic treatment
- Super-infection defined as new infection at a different anatomical site
- Suspected antibiotic adverse reactions
- Time to 'fit' for hospital discharge

The 90-days all-cause mortality will also be analysed as secondary outcome using linked data, for example, from NHS Digital and the Intensive Care National Audit and Research Centre.

Analysis methods

Participants' baseline characteristics and outcomes will be summarised mean and standard deviation if data are continuous or frequency and percentage if data are categorical. The median and interquartile range will be presented if data are non-normal.

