The primary effectiveness analyses will assess whether any of the biomarker interventions are better than standard care. The primary analysis approach for the duration of antibiotics will be intention-to-treat (ITT). ITT analysis will consist of all randomised patients and will assess the effect of treatment assignment. For the ITT analysis, linear mixed effects regression models will be fitted to estimate the treatment effect having adjusted for age, gender and the stratification variables (sepsis severity, recruiting centre (random effect) and surgery within the last 72 hours). After fitting the model, we will investigate the validity of the assumption of normality. Alternative methods of analyses will be considered if the distribution of the primary effectiveness outcome is non-normal. In this trial, participants may die before antibiotic therapy is discontinued. In such cases the outcome is undefined and is referred to as 'truncated by death'. A crude comparison between the survivors on each treatment arm may give rise to biased outcome comparisons. Therefore, we will consider undertaking some sensitivity analyses to estimate treatment effect having account for the deaths. This will explore different approaches to analysis of ICU trials, that allow incorporation of multiple relevant outcomes, including death, into a single overall measure (e.g., the win ratio⁸, global ranking score⁹, and weighted composite outcome¹⁰).

The primary safety outcome (28-day all-cause mortality) is based on assessing non-inferiority and we specify the null hypothesis that the biomarker interventions are much worse compared with standard-of-care. The primary safety outcome will be analysed using mixed effect logistic regression models, using the same adjustments variables as the primary effectiveness analysis. We will derive risk difference from the fitted logistic regression model to compare the non-inferiority margin for the safety outcome. The unadjusted and adjusted estimates and the 95% confidence intervals will be compared with the non-inferiority margin to accept/reject the null hypothesis. Therefore, our primary effectiveness outcome (antibiotic duration) will not provide all the information as regards the treatment effect. Safety (28-day all-cause mortality) is paramount - only if an intervention arm is not worse than the control (standard care only) will it be acceptable.

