Secondary outcomes will be assessed using an ITT approach. Continuous secondary outcomes will be analysed in the same way to the primary outcome and the categorical outcomes will be assessed using mixed effects logistic regression models. Time-to-event outcomes will be analysed using Cox

proportional hazards models. For all analyses, the adjusted effect estimates will be presented along with their associated 95% confidence interval (CI). In addition, the primary outcomes will also be analysed using Bayesian method as secondary analysis considering both non-informative and informative priors.

Exploratory sub-group analyses for primary effectiveness outcome will be reported using 99% confidence intervals. Linear mixed effect regression will be used with interaction terms (treatment group by sub-group) to estimate sub-group effects. The following sub-groups selected from a recent report about the management of infection causing sepsis in the NHS will be explored:

- Community-acquired pneumonia (CAP)
- Hospital-acquired pneumonia (HAP)
- Urinary tract infection (UTI)
- Intra-abdominal infection
- Infection with positive blood culture

In addition, community acquired, hospital acquired infections and SARS-COV-2 will be analysed as subgroup. Moreover, we will do the following subgroups analysis

- Sepsis vs Septic Shock
- Ward vs ICU where the intervention was stopped
- Surgery vs non-surgery on previous 72 hours

An exploratory analysis will be done to investigate weekend effect on the primary effectiveness outcome, the total duration of antibiotic treatment to 28 days from randomisation. Monitoring of the protocol processes and compliance measures is important in this trial (as detailed in section 4). These measures will be monitored and reported to the DMC throughout the trial. A final summary of the protocol processes and compliance will be presented at the end of the trial.

Handling missing data

Every effort will be made to minimise missing data both in baseline and outcome in the trial. Missing data will be assessed carefully. For the primary outcome (duration of antibiotics), start and stop dates for each course of antibiotics are required in order to compute the total duration for each participant. There will be no missing for start dates as the start dates and times will be the

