randomisation dates and times. In the event that stop dates are unobtainable and thus missing, we will first look to see if the participant either withdrew completely or died. If so, we will use the withdrawal/death date as the stop date to estimate the duration for a particular course of antibiotics. If they did not withdraw or die, then we would impute the duration for that particular course of antibiotics using the mean duration of all antibiotics for the participant.

The SOFA score is to be collected baseline at day 3 and day 7, however, date may not be available on these particular days hence this score would be missing. In this situation, we'll use the value from the day before. If this is not available, then we'll use the value of the day after. If neither are available, then the value for that particular day will be missing.

Additional analyses

The primary analysis looks at the total duration of antibiotic days from randomisation to day 28. However, it is also of interest to assess the duration of antibiotics during the intervention phase only i.e., when the biomarker guidance is in use, and also from randomisation to ICU discharge. Therefore, additional analyses will estimate the treatment effect for the duration of antibiotic days during the intervention phase only and also to the point of ICU discharge. Similarly, we will also estimate the same treatment effects for the daily defined dose (DDD) secondary outcome.

The impact of COVID-19 pandemic on the trial will be assessed on completion of the trial. The baseline demographics and primary outcomes for participants recruited before COVID-19 will be compared to those recruited during COVID-19. The objective is to assess if there is any change in the population considered for the trial. In addition, for participants recruited during the COVID-19 pandemic period, baseline demographics and primary outcomes will be compared for COVID positive versus COVID negative participants. We also perform a sensitivity analysis by dropping COVID positive participants to see if COVID pandemic has an impact on the trial. We will do a sensitivity analysis to account for the non-compliant sites with PCT testing during intervention and follow-up phase. The plan is to run the primary outcome analysis excluding the non-compliant sites and see if any difference between the arms.

Safety

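### The ward-versus-ICU subgroup is defined by where the intervention stopped, which treatment can change, so its interaction is not a randomised comparison

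*SAP*

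**What the plan says.** The exploratory subgroups are in the SAP under Analysis methods. The outcome and interval level are set by "Exploratory sub-group analyses for primary effectiveness outcome will be reported using 99% confidence intervals", and the model by "Linear mixed effect regression will be used with interaction terms (treatment group by sub-group) to estimate sub-group effects". The last three subgroups listed are sepsis against septic shock, "Ward vs ICU where the intervention was stopped", and surgery or not in the previous 72 hours. The first and third are stratification factors under Trial design, so they are fixed at randomisation. The middle one is not, yet it gets the same model with no baseline definition and no caveat.

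The outcome, under Outcome definitions, is "the sum of the duration of each course of antibiotics administered from randomisation to day 28". The Background gives the purpose of biomarker guidance as "to personalise antibiotic duration which could lead to reductions in population antibiotic burden". Additional analyses describes the period under guidance as "duration of antibiotics during the intervention phase only i.e., when the biomarker guidance is in use". The SAP does not say which event ends that period.

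**The concern.** A subgroup comparison keeps the protection of randomisation when membership is fixed before treatment can act. Here membership depends on whether stopping comes before or after ICU discharge. If guidance brings stopping forward, some participants who would have stopped on the ward now stop in ICU. Membership is then affected by treatment and also tied to the outcome, because short courses tend to end in ICU and long ones on the ward. A change in ICU stay would move participants between strata in the same way.

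The SAP recognises this kind of problem for deaths: "A crude comparison between the survivors on each treatment arm may give rise to biased outcome comparisons". It gives no such warning here. At stake is a reported difference between care settings that partly or wholly reflects who moved from one stratum to the other.

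**Working it through.** The SAP gives no figure for this subgroup, so there is nothing to reproduce. The size can only be illustrated.

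**Inputs from the SAP (Sample size, Trial design).** Mean duration 7 days, SD 6, target difference 1 day, total 2760 allocated 1:1:1, 5% withdrawal. Per arm 2760 / 3 = 920; evaluable 920 x 0.95 = 874.

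**Assumptions not in the SAP.** The intervention ends when antibiotics stop. ICU stay L is unaffected by arm in steps 1 to 4. A participant with duration D counts as ICU if D <= L, otherwise ward.

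**Definitions.** The apparent effect in a stratum is the mean duration of biomarker participants observed there minus that of controls observed there. The true effect is the mean within-person change among those whose location without the intervention would be that stratum.

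**1. Uniform reduction, gamma model.** D has mean 7, SD 6 (shape (7/6)^2 = 1.36). L has mean 6, SD 5 (shape (6/5)^2 = 1.44), independent of D. Each duration falls by 1 day, not below zero, so the overall effect is about -0.97.

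| | ICU | Ward | ICU minus ward |
|---|---|---|---|
| True | -0.93 | -1.00 | +0.07 |
| Apparent | -0.81 | -0.19 | -0.62 |

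The share stopping in ICU rises from 45.7% to 52.9%, or 7.2 percentage points. Those who move would have stopped soon after ICU discharge. Their departure leaves the longer courses on the ward and hides most of the ward effect.

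**2. Uniform reduction, lognormal model.** Same mean and SD, capped at 28 days; median ICU stay 4, 6 or 8 days; log-SD 0.8; correlation 0 or 0.4 between the underlying normal variables.
- True effects: -0.98 to -1.00 in both settings.
- Apparent effects: -0.91 to -1.10 in ICU and -0.19 to +0.29 on the ward.
- Spurious interaction: -0.71 to -1.28 days.
- ICU share: up by 6 to 12 percentage points.

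With 874 evaluable per arm, this interaction would be nominally significant with probability 0.14 to 0.47 at the 1% level, which matches the planned 99% intervals. For example, at median ICU stay 6 days and correlation 0, the interaction is -0.78 with standard error 0.49. Then z = 0.78 / 0.49 = 1.59, and the chance of exceeding 2.576 is about 0.17.

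**3. Proportional reduction of about 1 day overall.** Longer courses lose more days, so a difference between settings is expected.

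| Model | True ICU / ward (gap) | Apparent ICU / ward (gap) |
|---|---|---|
| Gamma | -0.51 / -1.41 (0.90) | -0.27 / -1.15 (0.88) |
| Lognormal, median 6, correlation 0 | -0.64 / -1.40 (0.76) | -0.44 / -1.04 (0.60) |

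In the gamma model the effects shrink by 0.51 - 0.27 = 0.24 and 1.41 - 1.15 = 0.26 day, and the gap is almost unchanged. In the lognormal case the gap is understated by 0.16 day.

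**4. No effect on duration or ICU stay.** Membership is the same in both arms, bias is zero, and rejection is at the nominal 5% and 1%.

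**5. No effect on duration, ICU stay one day shorter on average (gamma model).** Scaling every stay gives -0.35 in ICU and -0.34 on the ward. Subtracting a flat day gives -0.07 and -0.68. The truth is zero in both strata; the pattern depends on how stay is shortened.

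**The case against.** The strongest objection concerns the link between stopping location and outcome. The SAP never says that the intervention ends when antibiotics stop. Withdrawal and follow-up lists other ways of leaving it, including clinical team decision, futility and a need for more than 21 days of antibiotics. The endpoint also adds restarts, readmission courses and discharge antibiotics. The simulations classify participants by total duration and may therefore overstate the coupling. This stands against the exact figures. It does not rescue the variable, which is post-randomisation on any reading.

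The analysis is labelled exploratory, with 99% intervals, and is one of about eleven subgroups. That limits its weight and justifies a modest rating. Wider intervals deal with chance and multiplicity, not with strata that differ between arms.

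A reader might infer more than the documents support:
- That the bias is present whatever the treatment does. Step 4 shows it is not.
- That any difference between ward and ICU would be false. Under a proportional reduction it is partly or wholly real.
- That shorter ICU stay would produce a similar false benefit in both settings. Step 5 shows this depends on the form of shortening, and the SAP assumes no such effect.
- That "Critical care origin" or admission category could replace the subgroup. Template Table 4 defines the first as where the patient came from and the second as medical or surgical type. Neither identifies ward or ICU delivery.

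**Conclusion.** The point holds in conditional form. Under the trial's own hypothesis of earlier stopping, or if ICU stay changes, membership is affected by treatment, and the within-stratum effects and their interaction are not randomised comparisons. If treatment changes neither, they are unbiased.

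Under a uniform one-day reduction the spurious interaction is about -0.6 day in the gamma model and -0.7 to -1.3 days in the lognormal range, comparable with the 1-day target difference. Under a proportional reduction the main fault is attenuation, about 0.25 day in the gamma model. These sizes rest on assumed ICU stay and on the assumed link between stopping antibiotics and ending the intervention. They show direction and plausible range only.

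The consequence is confined to one exploratory subgroup. The primary intention-to-treat results for duration and 28-day mortality are unaffected.

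**What to change.** Remove this item from the treatment-by-subgroup interaction analyses. Report where the intervention stopped as a descriptive table by arm, with no treatment-effect estimate and no interaction test.

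If a care-setting subgroup is wanted, define it only by care location or level at randomisation, where that is recorded. Additional analyses already plans duration during the intervention phase and to ICU discharge, which partly addresses setting without splitting participants by stopping location.

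The cost is one line of SAP text and one descriptive table. Template Table 24 has no row for this subgroup, so that shell need not change, and the descriptive table needs no new data. The trial gives up one exploratory comparison.

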The ADAPT-Sepsis is a multi-centre three-arm randomised controlled trial with internal pilot. Participants are randomly allocated using a ratio 1:1:1 to CRP: PCT: Usual care. A computerised minimisation randomisation system was used, created by the Warwick Clinical Trials unit, to randomise participants. The randomisation allocation was made following consent processes and baseline assessments. Stratification factors were (i) sepsis severity (sepsis or septic shock), (ii) recruitment centre and (iii) surgery within the last 72 hours or not.

Primary and secondary outcomes

The primary outcomes are effectiveness outcome of total duration of antibiotics used to 28 days post randomisation and safety outcome of 28 days all-cause mortality. Secondary outcomes include escalation of care/re-admission; infection re-lapse/recurrence; dose of antibiotics; length and level of critical care stay, length of hospital stay, and 90-days all-cause mortality.

Sample size

A total sample size of 2760 would be able to detect both a mean of 1-day reduction in antibiotic use duration (using a mean antibiotic duration of 7 days, a pooled standard deviation of 6 days, 90% power, a significance level of 5%, with a 5% withdrawals rate) and a non-inferiority safety margin of 5.4 % (using a 1-sided significance level of 2.5%, 90% power and 5% withdrawal rate) assuming 28-day mortality is 15%.

Timing of final analysis

The end of the trial is defined when the last recruited participant completed 28-days follow-up post randomisation. Once all the data have been entered onto the database, the data will be fully validated and cleaned after which the database will be locked, and the final analyses will be undertaken.

Timing of outcome assessments

Primary and secondary outcome data will be collected daily from randomisation until hospital discharge. Data will also be collected post hospital discharge up to 28-days post randomisation. All-cause mortality

will be collected at 90 days using linked data. Any SAE's will also be reported up to 28 days post-randomisation.

Reporting of results

All primary and secondary clinical effectiveness outcomes will be reported in an earlier publication, with process of care and health economics outcomes reported in subsequent publications, when all the data are available.

In addition, the sub-study, RISC-sepsis will also be reported in a further publication (and has its own approved statistical analysis plan).

Statistical principles

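### A missing stop date becomes the death date with no check that the drug was still being given, so courses that ended earlier are scored too long; the likely effect on the arm difference is small

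*SAP*

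**What the plan says.** The primary effectiveness outcome (SAP, Outcome definitions) is "the sum of the duration of each course of antibiotics administered from randomisation to day 28". It counts courses restarted in hospital, given on readmission or continued after discharge, provided they fall within the 28 days.

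The SAP's Handling missing data section sets a two-step rule for a missing stop date. First: "In the event that stop dates are unobtainable and thus missing, we will first look to see if the participant either withdrew completely or died". Then: "If so, we will use the withdrawal/death date as the stop date to estimate the duration for a particular course of antibiotics". For everyone else, the plan is to "impute the duration for that particular course of antibiotics using the mean duration of all antibiotics for the participant".

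Two other statements bear on the rule:

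- Timing of outcome assessments: "Primary and secondary outcome data will be collected daily from randomisation until hospital discharge". A last recorded antibiotic day should therefore often exist for inpatients.
- Withdrawal and follow-up: "At 90 days, only all-cause mortality data will be collected using NHS digital" and a second national source. Some deaths will therefore be known that fall after the outcome window has closed.

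The missing-data rule does not ask whether the drug was recorded as given near death. It sets no maximum gap, and it does not say that the death must fall by day 28.

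**The concern.** A course cannot run beyond death, so the death date is the latest possible stop date. Using it as the estimate is right for someone who died on the drug and too long for anyone whose course ended earlier. The error for a death therefore has one direction. (This does not carry over to withdrawal, because a course may continue after a participant withdraws.)

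For affected participants the score no longer measures antibiotic use. It measures time to death, which belongs to the other primary outcome. A course stopped early and a course stopped late score the same, so any treatment contrast in that course is lost. A survivor with the same gap in the record is handled by a different rule.

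If such courses were common, or more common in one arm, the primary effectiveness outcome would carry extra days, extra variance and possibly bias. The sensitivity analyses for death in Analysis methods would not show this. They are only to be considered, they address truncation by death, and they do not vary the filled stop date.

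**Working it through.** The SAP gives no figure for missing stop dates, so there is none of its own to reproduce here.

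**Inputs from the SAP (Sample size):** 28-day mortality 15%; mean duration 7 days; SD 6 days; target difference 1 day; total 2760 over three arms with 5% withdrawal, i.e. 920 × 0.95 = 874 per arm.

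**Assumed, not in the SAP:** *f*, the share of deceased participants with a missing stop date on a course that ended earlier; *g*, the mean gap in days from true stop to death; the distribution of death times; late mortality.

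**1. Single participants.** One course starting at randomisation, with the day-28 window applied:

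| True stop | Death | Scored | Excess |
|---|---|---|---|
| day 5 | day 12 | 12 | 7 |
| day 5 | day 20 | 20 | 15 |
| day 7 | day 27 | 27 | 20 |
| day 5 | day 60 | 28 | 23 |

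**2. Mean excess per affected participant.** Let death be uniform over days 3–28 and the true stop be day *s*, or death if earlier. The mean excess is (28 − *s*)² / 50:

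- *s* = 3: 625 / 50 = 12.5 days
- *s* = 7: 441 / 50 = 8.8 days
- *s* = 10: 324 / 50 = 6.5 days

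**3. Inflation of an arm mean** = 0.15 × *f* × mean excess:

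- low: 0.15 × 0.05 × 6.5 = 0.05 day
- high: 0.15 × 0.20 × 12.5 = 0.38 day

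**4. Deaths after day 28.** Assume a further 3–6% die between days 29 and 90, 5–10% of them have a missing stop date, and the true stop was day 7. With the window applied the excess is 28 − 7 = 21 days:

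- low: 0.03 × 0.05 × 21 = 0.03 day
- high: 0.06 × 0.10 × 21 = 0.13 day

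**5. Effect on the arm difference.**

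- Equal *f* in all arms: the 1-day contrast is lost in a fraction 0.15 × *f* of participants. At *f* = 10% the loss is 0.15 × 0.10 × 1 = 0.015 day.
- *f* differing by 10 points between arms, *g* = 7: 0.15 × 0.10 × 7 = 0.105, about 0.11 day, in either direction.
- Mortality differing by the full 5.4-point non-inferiority margin, *f* = 10%, mean excess 8.8: 0.054 × 0.10 × 8.8 = 0.05 day.

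**6. Power for 1 day at 874 per arm, two-sided 5%.** With *p* = 0.15 × *f*, take the difference as 1 − *p* and the SD as √(36 + *p*(1 − *p*)*g*²):

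- no filled dates: SD 6, power 93.6%
- *f* = 10%, *g* = 7: SD 6.06, power 92.5%
- *f* = 20%, *g* = 14: SD 6.46, power 88.1%

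**The case against.** The strongest reply has four parts.

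- **The rule is a last resort.** It applies only when the stop date is unobtainable, after efforts to limit missing data, and antibiotic use is collected daily in hospital. In the case it most naturally covers, a participant who dies while still on treatment, the fill is exact. This stands. The rate of affected courses is unknown, and the 5–20% used above is an assumption.
- **The outcome is already limited to 28 days.** A reader might infer that a death on day 60 scores 60 days. On the assumptions of step 4, with late deaths uniform over days 29–90, the mean excess would then be 52.5 days and the arm mean would rise by 0.08–0.32 day. The document does not support that. Outcome definitions, Additional analyses and Table 21 all limit the outcome to day 28, and a rule that supplies a stop date does not redefine the window. What remains is that the rule does not repeat the limit.
- **The analysis compares arms.** A reader might take 0.05–0.38 day as bias in the treatment effect. It is inflation of each arm's mean, and most of it cancels when missingness is similar across arms. This also stands.
- **If daily records show the last day of a drug, its stop date is not missing; if they do not, no better fill exists.** This is only partly right. A last recorded day can bound a course whose formal stop date was never entered. However, the SAP does not say that the daily form records each drug separately, so the fix needs a fallback.

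**Conclusion.** The point holds as a gap in the missing-data rule. For a participant who died, the fill is exact or too long and never too short, and nothing in the rule separates the two cases. The arm mean rises by about 0.05–0.38 day if mortality is 15%, 5–20% of the deceased are affected, deaths are uniform over days 3–28 and true stops fall on days 3–10. The upper end needs 20% affected and every true stop on day 3. Deaths after day 28 add at most about 0.03–0.13 day within the window, under the late-mortality assumptions above.

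The effect on the planned comparison is smaller: about 0.015 day of dilution at 10% affected with equal missingness, or about 0.11 day either way with a 10-point imbalance and a 7-day gap, against a target of 1 day. The document does not show that the primary comparison is materially distorted, and this point should not be read that way. The correction is worth making because the frequency is unknown and the rule ties one primary outcome to the timing of the other.

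**What to change.** Amend the rule for participants who died and leave the rules for withdrawals and survivors unchanged. Suggested wording:

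*If the stop date is missing and the participant died, use the death date only if the drug was recorded as given on the day of death or the day before. Otherwise use the last day the drug was recorded as given or, for a course continued after discharge, the end of the prescribed course where known, never later than death or day 28. If no such record exists, keep the death date, limited to day 28. Report the death-date fill for all such courses as a sensitivity analysis.*

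The discharge clause matters: a plain last-recorded-day rule would cut post-discharge courses at discharge, although the outcome definition counts them. Reporting the number of filled stop dates by arm would also show whether missingness was balanced.

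The cost is a few sentences in the SAP and a small extra derivation from records. The downside is possible slight understatement where recording stopped before the drug did.
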